6.3.8 Visit 08, Final Study Visit, Day 181 (± 7 days), Clinic Visit

The following activities will be performed at Visit 08.

- Obtain interim medical history by interview of subjects and note any changes since the previous clinic visit.
- Obtain interim sexual history to identify any new sexual partners since the last study visit
- Record all concomitant medications on the appropriate eCRF.
- Assess all AE/SAEs and record them on the appropriate eCRF.
- Obtain vital signs including oral temperature, blood pressure, and pulse, if indicated based on review of complete medical history.
- A targeted physical examination will be performed, if needed, by a study clinician licensed to make medical diagnoses and listed on Form FDA 1572 as the site PI or sub-investigator, if indicated based on review of complete medical history.
- Collect venous blood for RPR and HIV-1/2 antibody testing
- Collect pharyngeal and rectal swabs for NAAT for GC and CT
- Collect urine for NAAT for GC/CT from male subjects
- Collect a self-collected vaginal swab for NAAT for GC/CT from female subjects
- Collect blood samples for immunologic assays as described in the Schedule of Events ([Appendix A](#))
- Collect rectal and oropharyngeal mucosal secretion samples for immunologic assays as described in the Schedule of Events ([Appendix A](#))
- From female subjects, collect vaginal mucosal secretion samples for immunologic assays as described in the Schedule of Events ([Appendix A](#))

6.3.9 Early Termination Visit

The following activities will be performed at the early termination visit for subjects who withdraw, or are withdrawn or terminated from this trial:

- Obtain interim medical history by interview of subjects and note any changes since the last study visit.
- Obtain interim sexual history to identify any new sexual partners since the last study visit
- Record all concomitant medications on the appropriate eCRF.
- Assess all AE/SAEs and record them on the appropriate eCRF.
- Obtain vital signs including oral temperature, blood pressure, and pulse, if needed.
- Perform a targeted physical examination, if indicated based on review of complete medical history.
- Examine vaccination site for local reactions if visit occurs ≤ 7 days after last injection.
- Assess for reactogenicity phenomena through subject interview and review memory aid if visit occurs ≤ 7 days after last injection.
- Perform a urine pregnancy test on all female subjects of childbearing potential (if indicated)
- If subject allows, obtain blood samples for immunologic assays appropriate to that visit if visit occurs within window of a regular study visit as described in the Schedule of Events ([Appendix A](#)).
- If subject allows, collect rectal and oropharyngeal mucosal secretion samples for immunologic assays appropriate to that visit if visit occurs within window of a regular study visit as described in the Schedule of Events ([Appendix A](#)).
- If subject allows, from female subjects, collect vaginal mucosal secretion samples for immunologic assays appropriate to that visit if visit occurs within window of a regular study visit as described in the Schedule of Events ([Appendix A](#)).

6.4 Unscheduled Study Visits

Unscheduled visits may occur at any time during this trial. Labs may be drawn at PI discretion. Any of the following activities may be performed:

- Obtain interim medical history by interview of subjects and note any changes since the last study visit.
- Record all concomitant medications on the appropriate eCRF.
- Obtain vital signs including oral temperature, blood pressure, and pulse, if indicated.
- Perform a targeted physical examination, if indicated based on review of complete medical history.
- Examine vaccination site for local reactions if visit occurs ≤ 7 days after study vaccination
- Assess for reactogenicity phenomena through subject interview if visit occurs ≤ 7 days after last injection.
- Obtain blood for safety if needed.
- Perform a urine pregnancy test on all female subjects of childbearing potential (if indicated).
- Assess all AE/SAEs and record them on the appropriate eCRF.

6.5 Protocol Deviations

A protocol deviation is any noncompliance with the clinical trial protocol, GCP, or protocol-specific MOP requirements. The noncompliance may be either on the part of the subject, the investigator, or the study site staff. As a result of deviations, corrective actions should be developed by the site and implemented promptly. It is the responsibility of the site PI and other study personnel to use continuous vigilance to identify and report protocol deviations. All individual protocol deviations will be addressed in subject study records. All protocol deviations, either individual, product, or site-specific will be collected and the record stored at the study site. Protocol deviations must be sent to the local IRB/IEC per its guidelines and will be reported to the sponsor. The site PI and other study personnel are responsible for knowing and adhering to their IRB/IEC requirements.

7 DESCRIPTION OF CLINICAL AND LABORATORY EVALUATIONS

7.1 Clinical Evaluations

- Complete medical history will be obtained by interviewing the subjects at the first study visit. Subjects will be queried regarding a history of significant medical disorders of the head, eyes, ears, nose, throat, mouth, cardiovascular system, lungs, gastrointestinal tract, liver, pancreas, kidney, urologic system, nervous system, blood, lymph nodes, endocrine system, musculoskeletal system, skin, and genital/reproductive tract. A history of any allergies, cancer, immunodeficiency, psychiatric illness, substance abuse, and autoimmune disease will be solicited. At subsequent follow-up visits, an interim medical history will be obtained by interview of the subjects noting any changes since the previous clinic visit.
- Concomitant medications will be collected as described in [Section 7.1.2](#).
- At the first screening visit (Visit 00A), a physical examination will be performed by a study clinician licensed to make medical diagnoses and listed on Form FDA 1572 as the site PI or sub-investigator. For all subsequent visits, a targeted physical examination may be performed by a study clinician licensed to make medical diagnoses and listed on Form FDA 1572 as the site PI or sub-investigator, if indicated based on subject's interim medical history.
- Vital signs (oral temperature, pulse, and blood pressure) will be collected at each study visit if indicated. Vital signs assessed on the screening visits (V00A and V00B) will be considered as baseline. Subjects must not eat or drink anything hot or cold, or smoke within 10 minutes before taking oral temperature. In the event of an abnormal heart rate or blood pressure due to physiological variation or activity, the subject may rest for 10 minutes in a quiet room, and then blood pressure and/or heart rate may be re-measured. The repeated measurement may be used to determine eligibility per the judgement of the investigator.
- Height and weight will be collected on the screening visit to determine BMI.
- Pre-administration reactogenicity assessments will be performed before each vaccination. A subject with mild (Grade 1) pre-administration reactogenicity which is transient, resolving, or clinically insignificant may be vaccinated at the investigator's discretion.

- Subjects will be observed in the clinic for ≥ 15 minutes after each vaccination. The vaccination site will be examined, post-administration reactogenicity assessments will be performed, and any AE/SAEs will be assessed and recorded on the appropriate eCRF before discharge from the clinic.
- All subjects will complete an electronic memory aid (with paper back up) on the day of each vaccination through seven days following each vaccination. Subject memory aids will be reviewed with the subjects for AEs (solicited injection site and systemic reactions, and unsolicited AEs). In addition, after each vaccination, whenever the subject is seen in the clinic, solicited and unsolicited reactogenicity and AEs will be reviewed.
- Reactogenicity assessments will include an assessment of solicited AEs occurring from the time of each vaccination through seven days following each vaccination, which include injection site reactions (pruritus, erythema, ecchymosis, induration/swelling, pain, and tenderness) and systemic reactions (fever, chills/shivering/sweating, fatigue, malaise, myalgia and arthralgia (exclusive of the injection site), headache, and nausea).

7.1.1 Research Procedures

Oropharyngeal mucosal secretion sampling

Trained, delegated study staff will be performing all oropharyngeal secretion (saliva) sampling procedures. Saliva will be collected and stored in the appropriate container. Instructions for saliva collection, handling, and storage are included in the MOP.

Vaginal mucosal secretion sampling

A trained, delegated clinician will be performing all vaginal mucosal sampling procedures with the assistance of a study coordinator utilizing a lubricated speculum and light source. Vaginal mucosal secretion samples will be collected and stored in the appropriate container. Instructions for vaginal secretion sample collection, handling, and storage are included in the MOP.

Rectal mucosal secretion sampling and biopsy

A trained, delegated clinician will be performing all rectal mucosal sampling procedures with the assistance of the study coordinator.

All subjects will have rectal mucosal secretions sampled utilizing a disposable anoscope and a light source. A lubricated anoscope will be inserted into the anus and 2-3 swabs or wicks will be used to collect secretions from the bowel wall for antibody measurements.

For subjects in the rectal mucosal biopsy cohort, a rigid sigmoidoscope, light source, and jumbo biopsy forceps will be utilized. Following rectal mucosal secretion sampling, without the administration of any previous enemas or other preparation, a rigid sigmoidoscope will be inserted and 8-12 adequate ~1.0 millimeter (mm) thick biopsy specimens will be taken from normal-appearing rectal mucosa approximately 10 cm above the external anal aperture using flexible sigmoidoscopic forceps mounted on a semi-flexible rod. All biopsy specimens will be coded with a unique numeric identifier such that the laboratories that receive the specimens will be unable to link them back to the study participants. The biopsy specimens will be placed in phosphate-buffered saline (PBS) and transported to a lab where the specimens will be processed for flow cytometry.

Twenty-four to forty-eight hours after the procedure, study personnel will call the participants who donated rectal biopsy samples and inquire about symptoms, complications, or adverse events related to study procedures. Participants who report symptoms suggestive of any significant complications will receive advice on seeking care and will be given referrals to appropriate healthcare professionals as needed. This follow-up may be completed over the phone or through electronic communication.

7.1.2 Assessment of Concomitant Medications/Treatments other than Study Product

Administration of any medications, therapies, or vaccines will be documented on the appropriate eCRF. Concomitant medications will include all current medications and non-study vaccinations taken within 30 days before signing the ICF through approximately 28 days after the last study vaccination, and for new-onset chronic medical conditions through the final study visit for each subject. Subjects who do not receive all vaccinations will have concomitant medications collected through approximately 28 days after the last vaccination, or early termination, whichever occurs first. Prescription and over-the-counter drugs will be included as well as herbals, vitamins, and supplements.

Use of new medication should prompt evaluation for the presence of a new diagnosis of chronic medical disease or condition.

Medications that might interfere with the evaluation of the study vaccines should not be used during the trial unless absolutely necessary. Medications in this category include the prohibited medications per the subject exclusion criteria (see [Section 5.1.2](#)). In addition, the site PI or appropriate sub-investigator may identify other medications that should not be used due to a risk to subject safety or assessment of reactogenicity and immunogenicity. Use of medications as prophylaxis before study vaccination is prohibited.

To the sponsor's knowledge, there are no known drug-vaccine interactions with the study vaccines and subjects are not being asked to discontinue current medications not listed in the exclusion criteria. In the event medical conditions dictate use of medications, subjects are encouraged to obtain adequate care, comply with the course of therapy as prescribed by their physician, and inform the Investigator as soon as practicable. Details of all medications taken during this trial (date, brand or generic name) will be recorded.

7.2 Laboratory Evaluations

Laboratory assays and blood volumes are detailed in [Appendix B](#).

7.2.1 Clinical Laboratory Evaluations

Screening

To be eligible for participation in this trial and receipt of the first vaccine, the subject's clinical screening lab evaluations (Visit 00A) must be confirmed to meet the subject inclusion criteria (see [Section 5.1](#)). All subjects will be screened for GC and CT infection at all relevant mucosal sites with NAAT. Female subjects will also be screened for *Trichomonas vaginalis* vaginal infection by NAAT. NAAT will be performed as follows:

- Rectal and pharyngeal swabs, and urine specimens will be obtained from male subjects
- Rectal and pharyngeal swabs, and self-collected vaginal swabs will be obtained from female subjects

Subjects will be screened for RPR and HIV-1/2 antibody. If a positive result on any of these screening tests occurs, the subject will be referred for appropriate follow-up and results reported as required by state law. These screening tests must be negative for the subject to be eligible to participate.

Urine pregnancy tests will be performed by the site laboratory at the screening visit (Visit 00A) and within 24 hours before initial vaccination (Day 1 (Visit 01)) on all female subjects of childbearing potential. Results must be negative and known before randomization on Day 1 (Visit 01) and before receipt of vaccination.

In the subset of participants who will undergo rectal mucosal biopsy, additional laboratory tests at the screening visit (Visit 00A) will include complete blood count (WBC, hemoglobin, PLT), PT and aPTT.

Follow-Up

Urine pregnancy tests will be performed by the site laboratory within 24 hours before second vaccination (Day 29 (Visit 04)) on all female subjects of childbearing potential. Results must be negative and known before receipt of vaccination.

Subjects will be re-screened for GC and CT infection at all relevant mucosal sites with NAAT prior to the second vaccination at Day 29 (Visit 04) and at the final study visit (Day 181 (Visit 08)) as follows:

- Rectal and pharyngeal swabs, and urine specimens will be obtained from male subjects
- Rectal and pharyngeal swabs, and self-collected vaginal swabs will be obtained from female subjects

Subjects will also be re-screened for RPR at Day 29 (Visit 04) and Day 181 (Visit 08). If a positive result on any of these screening tests occurs, the subject will be referred for appropriate follow-up and results reported as required by state law.

7.2.2 Research Assays

7.2.2.1 Antibody assays

Antibody assays will be performed at the study site ([name] laboratory) and will include:

- Measurement of IgG concentrations against GC antigens at mucosal sites (rectum, vagina, oropharynx) and in serum as described in the Schedule of Events ([Appendix A](#)) by enzyme-linked immunosorbent assay (ELISA)
- Measurement of IgA concentrations against GC antigens at mucosal sites (rectum, vagina, oropharynx) and in serum as described in the Schedule of Events ([Appendix A](#)) by ELISA
- Measurement of serum bactericidal antibody titers as described in the Schedule of Events ([Appendix A](#))
- Measurement of IgG concentrations against *N. meningitidis* antigens in serum as described in the Schedule of Events ([Appendix A](#)) by ELISA

7.2.2.2 Cell-mediated immunity assays

Cell-mediated immunity assays will be performed at the study site (Hope Clinic) and will include:

- Frequencies and function of memory B cells (MBC) specific for antigens from GC and *N. meningitidis* as described in the Schedule of Events ([Appendix A](#)) by ELISpot
- Frequencies and function of peripheral blood T cells specific for antigens from GC and *N. meningitidis* as described in the Schedule of Events ([Appendix A](#)) by ELISpot
- Frequencies, phenotype, and function of peripheral blood CD4+ and CD8+ T cells specific for antigens from GC and *N. meningitidis* as described in the Schedule of Events ([Appendix A](#)) by intracellular cytokine staining (ICS)
- Frequencies, phenotype, and function of rectal mucosal CD4+ and CD8+ T cells specific for antigens from GC as described in the Schedule of Events ([Appendix A](#)) by ICS

7.2.2.3 Bacterial adhesion assay

Serum for bacterial adhesion assays will be collected as described in the Schedule of Events ([Appendix A](#)). For samples scheduled to be collected during vaccination visits, samples will be collected before vaccination.

The bacterial adhesion assay will be performed at the study site ([name] laboratory). Instructions for specimen preparation, handling, storage, and labeling are included in the MOP.

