3.2.3 Exploratory

- To characterize the vaginal mucosal IgG antibody response to GC elicited by the 4CMenB vaccine as compared with the placebo vaccine in healthy adult subjects.
- To characterize the oropharyngeal mucosal IgG antibody response to GC elicited by the 4CMenB vaccine as compared with the placebo vaccine in healthy adult subjects.
- To characterize the serum IgA antibody response to GC elicited by the 4CMenB vaccine as compared with the placebo vaccine in healthy adult subjects.
- To characterize the mucosal IgA antibody response to GC elicited by the 4CMenB vaccine as compared with the placebo vaccine in healthy adult subjects.
- To characterize the systemic B cell responses to GC antigens elicited by 4CMenB vaccine as compared with the placebo vaccine in healthy adult subjects.
- To characterize the systemic T cell responses to GC antigens elicited by 4CMenB vaccine as compared with placebo vaccine in healthy adult subjects.
- To characterize the mucosal T cell responses to GC antigens elicited by 4CMenB vaccine as compared with the placebo vaccine in healthy adult subjects.
- To characterize the serum bactericidal antibody responses to GC elicited by 4CMenB vaccine as compared with the placebo vaccine in healthy adult subjects.
- To evaluate the impact of 4CMenB vaccine-induced antibodies on gonococcal adhesion to human cervical cells.

- To characterize immune responses to *N. meningitidis* elicited by the 4CMenB vaccine as compared with the placebo vaccine in healthy adult subjects for use as controls.

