3.3.3 Exploratory

- Rectal mucosal IgG concentrations (GMT) against GC antigens before and after vaccination in each treatment group
- Serum IgG concentrations (GMT) against GC antigens before and after vaccination in each treatment group
- Vaginal mucosal IgG concentrations geometric mean titer (GMT) against GC antigens before and after vaccination in female subjects in each treatment group
- Oropharyngeal mucosal IgG concentrations (GMT) against GC antigens before and after vaccination in each treatment group
- Serum IgA concentrations (GMT) against GC antigens before and after vaccination in each treatment group
- Rectal mucosal IgA concentrations (GMT) against GC antigens before and after vaccination in each treatment group
- Vaginal mucosal IgA concentrations (GMT) against GC antigens before and after vaccination in female subjects in each treatment group
- Oropharyngeal mucosal IgA concentrations (GMT) against GC antigens before and after vaccination in each treatment group

- Frequencies and function of memory B cells specific for antigens from GC before and after vaccination by ELISpot in each treatment group.
- Frequencies and function of peripheral blood T cells specific for antigens from GC before and after vaccination by ELISpot in each treatment group.
- Frequencies, phenotype, and function of peripheral blood CD4+ T cells specific for antigens from GC based on cytokine profile before and after vaccination by intracellular cytokine staining in each treatment group.
- Frequencies, phenotype, and function of peripheral blood CD8+ T cells specific for antigens from GC based on cytokine profile before and after vaccination by intracellular cytokine staining in each treatment group.
- Frequencies, phenotype, and function of rectal mucosal CD4+ T cells specific for antigens from GC based on cytokine profile before and after vaccination by intracellular cytokine staining in each treatment group.
- Frequencies, phenotype, and function of rectal mucosal CD8+ T cells specific for antigens from GC based on cytokine profile before and after vaccination by intracellular cytokine staining in each treatment group.
- Serum bactericidal antibody titers against GC before and after vaccination in each treatment group.
- Percent inhibition of gonococcal adhesion to human cervical cell line (ME180) by mucosal antibodies at Day 43 in each treatment group.

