3.3.2. Immunogenicity Outcomes

In the primary, secondary, and exploratory outcomes, the GMT for Enzyme-Linked Immunosorbent Assay (ELISA) will be calculated for Days 1, 29, 43, 57 and 181 for each treatment arm. The GMT is defined as:

$$GMT = \sqrt[n]{X_1 * X_2 * X_3 * \dots * X_n}$$

In practice, it is the equivalent of: $GMT = \text{Exp}\{[\log(X_1) + \log(X_2) + \dots + \log(X_n)] / n\}$

Where the X_1, X_2, \dots, X_n are the titers for each participant at a certain timepoint. A sample SAS code for calculating the geometric mean and the 95% confidence interval is shown below.

```
proc surveymeans  
  data=data geomean;  
  var variable;  
  run;
```

The geometric mean fold rise (GMFR) for ELISA titers will be calculated for Days 29, 43, 57, and 181 compared to baseline titer in each study arm. The fold change for each participant at each timepoint is calculated first by dividing the follow-up titer by the baseline titer, then the geometric mean and 95% confidence interval will be calculated for each treatment arm at each timepoint.

Similarly, the ratio of serum to mucosal (rectal, vaginal, and oropharyngeal) IgG will be calculated at each time point. The geometric mean and confidence interval will be calculated as above.

Percent inhibition of gonococcal adhesion to human cervical cell line by mucosal antibody is defined as:

$$100\% * [(Titer \text{ without mucosal antibody} - Titer \text{ with mucosal antibody}) / Titer \text{ without mucosal antibody}]$$

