4.5. Immunogenicity and Safety Variables

4.5.1. Immunogenicity Variables

See [Table 2](#) for the schedule of study procedures.

Immunogenicity testing will include antibody assays, cell-mediated immunity assays, and bacterial adhesion assays. Antibody assays will be performed to measure the IgG and IgA concentrations against GC antigens at mucosal sites (rectum, vagina, oropharynx) and in serum, serum IgG concentrations against *N. meningitidis* antigens by enzyme-linked immunosorbent assay (ELISA), and serum bactericidal antibody titers determined by assessing GC survival in the presence of a fixed concentration of human complement source and serially diluted sera in which complement has been heat inactivated. Cell-mediated immunity assays will be performed to measure frequencies and function of memory B cells (MBC) and peripheral blood T cells specific for GC and *N. meningitidis* antigens by ELISpot. Cell-mediated immunity assays will be performed to measure frequencies, phenotype and function of peripheral blood CD4+ and CD8+ T cells and rectal mucosal CD4+ and CD8+ T cells specific for GC antigens by intracellular cytokine staining (ICS). Similar assays will also be performed with peripheral blood CD4+ and CD8+ T cells specific for *N. meningitidis* antigens. A bacterial adhesion assay will be performed to measure the percent inhibition by mucosal antibodies of gonococcal adhesion to a ME180 human cervical cell line at Day 43 in each treatment group. Serum for systemic immunity assays will be collected at days 1 (pre-vaccination), 8, 15, 29, 36, 43, 57 and 181. Serum and mucosal (rectum, vagina, oropharynx) samples for antibody assays will be collected at days 1 (pre-vaccination), 29, 43, 57 and 181.

The immunogenicity variables are: Concentration of mucosal antibodies (IgG or IgA) against GC antigens at mucosal sites (rectum, vagina oropharynx) and serum antibodies (IgG or IgA) against GC antigens. These will be measured by ELISA from specimens collected at each visit (days 1, 29, 43, 57 and 181), and results will be reported as geometric mean titer and 95% confidence interval for each time point for the two treatment arms.

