- Frequencies and function of memory B cells and T cells from peripheral blood for GC and *N. meningitidis* antigens will be measured at each visit with ELISpot. The frequencies (cell count) will be reported. Frequencies and function of CD4+ and CD8+ T cells specific for GC and *N. meningitidis* antigens from peripheral blood, and GC antigens from rectal mucosae. These will be measured at each visit with ICS. Cell frequencies will be reported.
- Serum bactericidal antibody against GC and *N. meningitidis* will be measured and reported as geometric mean titer and 95% confidence interval for each time point for the two treatment arms.
- Inhibition of bacterial adhesion to a human cervical cell line (ME180) by mucosal antibodies will be measured by bacterial adhesion assay, and geometric mean titer and 95% confidence interval at each time point for two treatment arms will be reported.
- Other exploratory Immunogenicity outcomes measured by ELISA, ELISpot, and bacterial adhesion assays will be reported similarly.

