Same format for the following tables:

Table 43: Frequencies and Function of Rectal Mucosal CD4+ T Cells Specific for Antigens by Time Point and Treatment Group - ICS - Per-Protocol Population

Table 44: Frequencies and Function of Rectal Mucosal CD8+ T Cells Specific for Antigens by Time Point and Treatment Group - ICS - Immunogenicity Population

[note: The CD8 table should not contain IL17+ as cytokine]

Table 45: Frequencies and Function of Rectal Mucosal CD8+ T Cells Specific for Antigens by Time Point and Treatment Group - ICS - Per-Protocol Population

[note: The CD8 table should not contain IL17+ as cytokine]

Table 46: Percent Inhibition of Gonococcal Adhesion to Human Cervical Cell Line (ME180) by Mucosal Antibodies at Day 43

Population	Assay	Percent Inhibition (95% CI)	
		4CMenB	Placebo
Immunogenicity Population	N*	x	x
	BAA_1291	x(x , x)	x(x , x)
	BAA_20	x(x , x)	x(x , x)
Per-Protocol Population	N*	x	x
	BAA_1291	x(x , x)	x(x , x)
	BAA_20	x(x , x)	x(x , x)

*N =Number of participants in the certain Treatment Group for certain analysis population

Table 47: Summary of Categorical Sexual History Variables at Screening - All Enrolled Participants

Variable		Characteristic	4CMenB N=X		Placebo N=X		All Participants	
			n	%	n	%	n	%
Oral receptive	Yes/No	No	x	x	x	x	x	x
		Yes	x	x	x	x	x	x
	How often did the participant or the participant's partner use a condom or barrier for protection?	Always	x	x	x	x	x	x
		Sometimes	x	x	x	x	x	x
		Never	x	x	x	x	x	x
Oral active	Yes/No	No	x	x	x	x	x	x
		Yes	x	x	x	x	x	x
	How often did the participant or the participant's partner use a condom or barrier for protection?	Always	x	x	x	x	x	x
		Sometimes	x	x	x	x	x	x
		Never	x	x	x	x	x	x
Rectal receptive	Yes/No	No	x	x	x	x	x	x
		Yes	x	x	x	x	x	x
	How often did the participant or the participant's partner use a condom or barrier for protection?	Always	x	x	x	x	x	x
		Sometimes	x	x	x	x	x	x
		Never	x	x	x	x	x	x
Rectal insertive	Yes/No	No	x	x	x	x	x	x
		Yes	x	x	x	x	x	x
	How often did the participant or the participant's partner use a condom or barrier for protection?	Always	x	x	x	x	x	x
		Sometimes	x	x	x	x	x	x
		Never	x	x	x	x	x	x
Genital/vaginal	Yes/No	No	x	x	x	x	x	x
		Yes	x	x	x	x	x	x
	How often did the participant or the participant's partner use a condom or barrier for protection?	Always	x	x	x	x	x	x
		Sometimes	x	x	x	x	x	x
		Never	x	x	x	x	x	x

Note: N is the number of participants answered "Yes" to the question "Sexual intercourse in last 6 months?"

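### The adhesion-assay procedure names serum, but the endpoint is defined on mucosal antibodies with no site named; SAP 4.5.1 also gives it a geometric mean titer at each time point that percent inhibition does not support

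*Protocol*

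**What the plan says.** **Specimen.** Protocol 7.2.2.3 states: "Serum for bacterial adhesion assays will be collected as described in the Schedule of Events". It mentions no other specimen. The exploratory endpoint in protocol 3.3.3 is "Percent inhibition of gonococcal adhesion to human cervical cell line (ME180) by mucosal antibodies at Day 43 in each treatment group". SAP 3.2.3 repeats that endpoint. SAP 3.3.2 gives the formula, introduced by "Percent inhibition of gonococcal adhesion to human cervical cell line by mucosal antibody is defined as", and uses the titer with and without mucosal antibody. SAP 4.5.1 describes the assay the same way: "A bacterial adhesion assay will be performed to measure the percent inhibition by mucosal antibodies of gonococcal adhesion". SAP 8.3, the title of SAP Table 46 ("Percent Inhibition of Gonococcal Adhesion to Human Cervical Cell Line (ME180) by Mucosal Antibodies at Day 43") and SAP Listing 22 agree. The objective in protocol 3.2.3 is neutral: "To evaluate the impact of 4CMenB vaccine-induced antibodies on gonococcal adhesion to human cervical cells".

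**Summary statistic.** SAP 4.5.1 first places the assay at Day 43. Its later list of variables says "Inhibition of bacterial adhesion to a human cervical cell line (ME180) by mucosal antibodies will be measured by bacterial adhesion assay" and continues that "geometric mean titer and 95% confidence interval at each time point for two treatment arms will be reported". SAP 8.3, Table 46 and Listing 22 refer to percent inhibition at Day 43 only. The column heading of Table 46 is percent inhibition with a 95% CI and does not say which mean is used. SAP 6.1 restricts geometric means to non-zero values.

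**The concern.** Read literally, the procedure section supplies a specimen that does not fit the endpoint. Inhibition by serum antibody answers a systemic question, whereas the endpoint asks what antibody at the mucosa does. A result obtained on serum could not properly be reported under the title of Table 46. Even a reader who accepts the mucosal definition cannot tell from the documents whether rectal, oropharyngeal or vaginal secretions are meant.

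The SAP conflict is separate. Two programmers following different sections would produce different outputs. The one following 4.5.1 would apply a statistic that the variable does not support, and would look for time points at which the endpoint is not defined.

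**Working it through.** **1. Specimen and timing, side by side**

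| Place | Specimen | Timing |
|---|---|---|
| Protocol 7.2.2.3 | Serum | Deferred to the Schedule of Events |
| Protocol 3.3.3 | Mucosal antibodies | Day 43 |
| SAP 3.2.3 | Mucosal antibodies | Day 43 |
| SAP 3.3.2 (formula) | Mucosal antibody | Not stated |
| SAP 4.5.1 (assay description) | Mucosal antibodies | Day 43 |
| SAP 4.5.1 (variable list) | Mucosal antibodies | Each time point |
| SAP 8.3, Table 46, Listing 22 | Mucosal antibodies | Day 43 |

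Serum stands alone in the specimen column. Each time point stands alone in the timing column. No place names a mucosal site.

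**2. Does the schedule settle it?** Section 7.2.2.3 defers to the Schedule of Events. Appendix A lists mucosal sampling and a general serum antibody draw, with no adhesion row. Appendix B is organised by assay and also has none. The Visit 6 (Day 43) volumes in Appendix B are:

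- *N. gonorrhoeae*: serum IgG 8, serum IgA 8, memory B cell 24, T-cell ELISPOT 16
- T-cell ICS 32, bactericidal antibody 8
- *N. meningitidis*: serum IgG 8, memory B cell 16, T-cell ELISPOT 16

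8 + 8 + 24 + 16 + 32 + 8 + 8 + 16 + 16 = 136 mL, which reproduces the stated total. No blood is separately allotted to this assay. That does not exclude use of leftover serum.

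**3. Signs of carried-over text.** The two collection sentences in 7.2.2.3 nearly duplicate those for serum in 7.2.2.4, including the rule on sampling before vaccination. Vaccination is on Days 1 and 29, so that rule has no bearing on a Day 43 endpoint.

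**4. Range of the variable.** Let T0 be the titer without mucosal antibody and T1 the titer with it. SAP 3.3.2 gives

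PI = 100% × (T0 − T1) / T0 = 100% × (1 − T1/T0).

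- T1 < T0: PI is positive.
- T1 = T0: PI = 0.
- T1 > T0: PI is negative.

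With no true inhibition and ordinary assay noise, T1 falls on either side of T0, so zeros and negatives are to be expected. The logarithm of a negative value does not exist, and SAP 6.1 has no rule for one. A single zero would make a geometric mean zero, so SAP 6.1 excludes zeros.

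**5. Effect of excluding zeros.** Suppose a fraction f of an arm has PI = 0 and the rest average m. The average over everyone is (1 − f) × m. Over the non-zero values it is m, larger by a factor 1/(1 − f). The documents give no figure for f. Assuming 0.1 to 0.5, the factor runs from 1/0.9 = 1.11 to 1/0.5 = 2.00. If zeros are commoner on placebo, the placebo figure is raised more and the difference between arms shrinks.

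**6. Numbers if the specimen is vaginal.** From protocol Table 1, females are 8 + 12 = 20 on vaccine and 2 + 3 = 5 on placebo.

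**The case against.** **The laboratory would probably read it correctly.** One collection sentence stands against a consistent endpoint and SAP, and it looks carried over. Rectal, oropharyngeal and, in females, vaginal secretions are collected at Visit 6 whatever 7.2.2.3 says. Specimen handling is left to a manual of procedures that is not available here. This stands as a limit: the documents show an inconsistency, not that the assay will be run on serum. A reader might go further and infer that mucosal volume for the assay will be lost for good. That is not shown, because whether volume is set aside is unknown.

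**Serum may be intended as well.** The objective speaks only of vaccine-induced antibodies, so a serum version cannot be excluded. This stands, and it is why any serum version should be defined separately.

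**The geometric mean may refer to the titers inside the formula.** SAP 3.3.2 does call its inputs titers, and a GMT of those would be defined if they are positive. It would not be the endpoint, however, Table 46 has no place for it, and the conflict between each time point and Day 43 would remain.

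**Importance.** A reader might call this the only functional read-out at the mucosa. It is not: rectal CD4+ and CD8+ T-cell function is also an endpoint. At most it is the only functional mucosal *antibody* read-out, the bactericidal assay being on serum. A reader might also take Table 46 to promise 40 and 10 participants, but its N entries are placeholders. Nor does the cervical origin of ME180 show that vaginal secretions are meant.

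**Conclusion.** The point holds as two inconsistencies. First, protocol 7.2.2.3 names a specimen that does not match the endpoint in protocol 3.3.3 or any SAP description of the assay, and the mucosal site is left open. Second, the variable list in SAP 4.5.1 conflicts with the rest of the SAP on timing and names a summary that is undefined for negative percent inhibition and biased upward once SAP 6.1 removes the zeros.

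The effect is confined to one exploratory endpoint. Under SAP 6.2 exploratory assays depend on the interim immunogenicity results and are reported in an addendum to the study report. No primary, secondary or safety result changes. The size of the bias depends on how many participants show no inhibition, which the documents do not give. The 20 and 5 apply only if vaginal secretions are chosen. In that case the assay-specific population rule in SAP 6.3.1 already makes the restriction.

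The conclusion treats the mucosal definition as the intended one because the endpoint and every SAP description agree on it.

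**What to change.** - **Protocol 7.2.2.3:** name the mucosal secretion(s) tested, matching the endpoint in 3.3.3. If serum is also wanted, add it as a separate endpoint with its own time point(s).
- **Protocol Appendix B:** add a row for the adhesion assay at Visit 6.
- **SAP 4.5.1:** replace the geometric mean titer at each time point with arithmetic mean percent inhibition at Day 43 and its 95% CI, including zero and negative values. This fits the SAP's own practice: 6.1 uses the mean by default for continuous variables, and 8.3 uses it for cell frequencies reported as percentages.
- **SAP Table 46:** state that the figure is an arithmetic mean, since neither the table nor 3.3.2 says so now. If more than one site is tested, show each separately. No new population rule is needed for vaginal samples.

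The cost is wording in the two documents. No visit, procedure or sample is added, because the secretions are already collected at Visit 6.
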